8.6 Medical Device Product Complaints for Drug/Device Combination Products

Not Applicable.

8.7 Pharmacokinetics

8.7.1 Pharmacokinetic Sampling

The whole blood and serum tubes should be labelled before sampling. The information on the label should include but not limit to the protocol number, randomization number, period, sampling time point, primary or backup sample.

Sample Label

Bar code CHS-1420-10 Participant: 10XX PK sample: Day X-X h-A	Bar code CHS-1420-10 Participant: 10XX PK sample: Day X-X h-B	Bar code CHS-1420-10 Participant: 10XX PK sample: Day X-X h
--	--	--

The information is as follows:

Line 1: Bar code;

Line 2: Protocol No.;

Line 3: Participant random No.;

Line 4: Indication that samples for PK analysis, and sampling day and time point (A represents the primary sample and B backup sample, both of which are serum sample tubes. It is the whole blood sample tube without A or B).

The serum drug (adalimumab) concentration will be measured and a procoagulant will be used for blood samples.

Sample Collection: A total of twenty-four (24) blood samples for each participant will be collected for determination of serum drug concentrations at 0 h (within 30 minutes pre-dose) and 2 h (Day 1), 4 h (Day 1), 8 h (Day 1), 12 h (Day 1), 24 h (Day 2), 36 h (Day 2), 48 h (Day 3), 60 h (Day 3), 72 h (Day 4), 96 h (Day 5), 120 h (Day 6), 144 h (Day 7), 168 h (Day 8), 216 h (Day 10), 288 h (Day 13), 360 h (Day 16), 528 h (Day 23), 696 h (Day 30), 864 h (Day 37), 1032 h (Day 44), 1200 h (Day 51), 1368 h (Day 58), 1536 h (Day 65) post-dose. Approximately 3.5 mL of blood will be collected into vacutainer tubes containing the procoagulant followed by gentle inversions to get mixed up and then be left standing still till coagulation. If blood samples are obtained from an indwelling catheter rather than straight venipuncture, withdraw approximately 1 mL blood prior to obtaining the PK blood sample each time. After each blood collection, use an appropriate amount of

normal saline solution to seal the catheter.

Pre-handling of Samples: The coagulated blood samples will be centrifuged in a refrigerated centrifugue at 2-8°C. Serum will be transferred into two tubes – tube “A” for the primary assay sample and tube “B” as the backup sample. Serum will be stored in a freezer at -70°C (temperature range -90°C ~ -60°C) until shipment to the bioanalytical laboratory for analysis.

Refer to the sampling manual for detailed requirements regarding sample processing.

8.7.2 Sample Shipment and Storage

The serum samples to be tested will be transported by the cold chain logistics to Frontage Laboratories (Shanghai) Co., Ltd.. The temperature during the shipment will be monitored. Frontage Laboratories (Shanghai) Co., Ltd. is responsible for the preservation of the biosamples to be tested. The samples will be stored in a freezer (temperature range -80±10°C), and the preservation of the biosamples will be monitored and recorded according to the current specifications. Backup samples can only be transported and tested after the written approval of sponsor.

8.7.3 Bioanalysis

Serum Drug (adalimumab) concentration will be measured with the validated method by the analysts.

Method validation should be performed according to the relevant requirements ICH M10, which includes selectivity, lower limit of quantitation, calibration range (standard curve performance), accuracy, precision, matrix effect, stability in solution and biological matrix during storage and handling process, *etc.*

Sample analysis plan should be prepared prior to sample analysis. The entire analysis procedure should follow the laboratory SOPs and relevant guidelines.

Two hundred and thirty-eight (238) participants are to be enrolled. There are 24 sampling time points totally in the single-period parallel trial for each participant. Therefore, the expected number of primary samples is 5712, and incurred sample reanalysis (ISR) should be no less than 336.

8.8 Genetics

In course of the trial, sampling will be conducted on each participant for PK similarity assessment and immunogenicity comparison. And also blood will be collected for safety tests. The expected blood collection during the study before the last scheduled OPV for individual participants to be enrolled is listed as follows:

Study stage	Blood collection	Volume per test	Amount of blood loss	
			Male	Female
Screening	Antinuclear antibody test	4 mL	4 × 1 mL	4 × 1 mL
	Viral tests (HIV/HBV/HCV/syphilis)	4 mL	4 × 1 mL	4 × 1 mL
	Tuberculosis diagnosis	4 mL	4 × 1 mL	4 × 1 mL
	Biochemistry	4 mL	4 × 1 mL	4 × 1 mL
	Hematology	2 mL	2 × 1 mL	2 × 1 mL
	Coagulation function	3 mL	3 × 1 mL	3 × 1 mL
	Serum pregnancy test (only for females)	4 mL	--	4 × 1 mL
Check-in	Serum pregnancy test (only for females)	4 mL	--	4 × 1 mL
Test period	PK sampling	3.5 mL	3.5 × 24 mL	3.5 × 24 mL
	Blood withdrawn before PK sampling	1 mL	1 × 5 mL	1 × 5 mL
	Immunogenicity sampling	5 mL	5 × 4 mL	5 × 4 mL
	Safety tests - Biochemistry	4 mL	4 × 4 mL	4 × 4 mL
	Safety tests - Hematology	2 mL	2 × 4 mL	2 × 4 mL
	Safety tests - Coagulation function	3 mL	3 × 4 mL	3 × 4 mL
	Safety tests - Serum pregnancy test (only for females)	4 mL	--	4 × 4 mL
Amount of blood loss during the study			162 mL	186 mL

If warranted, participants may undergo additional blood samplings for screening and safety assessment at discretion of investigators.

The samples will be analyzed as per the laboratory requirements.

8.9 Biomarkers

Not Applicable.

8.10 Immunogenicity Assessments

The whole blood and serum tubes should be labelled before sampling. The information on the label should include but not limit to the protocol number, randomization number, period, sampling time point, primary or backup sample.

Sample Label

Bar code CHS-1420-10 Participant: 10XX IM sample: Day X-ADA	Bar code CHS-1420-10 Participant: 10XX IM sample: Day X-Nab	Bar code CHS-1420-10 Participant: 10XX IM sample: Day X-B	Bar code CHS-1420-10 Participant: 10XX IM sample: Day X
--	--	--	--

The information is as follows:

Line 1: Bar code;

Line 2: Protocol No.;

Line 3: Participant random No.;

Line 4: Indication that samples for immunogenicity assessment, and sampling day (ADA and Nab represents the primary assay samples and B for the backup sample, both of which are serum sample tubes. It is the whole blood sample tube without ADA, Nab or B).

The serum ADA/Nab will be determined and a procoagulant will be used for blood samples.

Sample Collection: A total of four (4) blood samples for each participant will be collected for determination of serum anti-drug antibodies (ADA) / neutralizing antibodies (Nab) at 0 h (within 30 minutes pre-dose) and Day 16, Day 30, Day 65 post-dose. The actual sampling time should be recorded. Approximately 5 mL of blood will be collected into vacutainer tubes containing the procoagulant followed by gentle inversions to get mixed up and then be left standing still till coagulation. If blood samples are obtained from an indwelling catheter rather than straight venipuncture, withdraw approximately 1 mL blood prior to obtaining the PK blood sample each time. After each blood collection, use an appropriate amount of normal saline solution to seal the catheter.

Pre-handling of Samples: The coagulated blood samples will be centrifuged in a refrigerated centrifuge at 2-8°C. Serum will be transferred into three tubes – tube “ADA and Nab” for the primary assay sample and tube “B” as the backup sample. Serum will be stored in a freezer at -70°C (temperature range -90°C ~ -60°C) until shipment to the bioanalytical laboratory for analysis.

Refer to the sampling manual for detailed requirements regarding sample processing.

The serum samples to be tested will be transported by the cold chain logistics to Frontage Laboratories (Shanghai) Co., Ltd.. in the same way as PK samples.

The serum ADA/Nab will be measured with the validated method by the analysts.

Two hundred and thirty-eight (238) participants are to be enrolled. There are 4 sampling time points totally in the single-period parallel trial for each participant. Therefore, the expected number of primary samples is 952 for ADA.

8.11 Medical Resource Utilization and Health Economics

Not Applicable.

9 STATISTICAL CONSIDERATIONS

Statistical analysis plan (SAP) should be prepared before statistical analysis. The statistics process should follow SOPs for statistical analysis and related guidance.

If modification of the finalized SAP is necessary, revisions should be clarified together with the sponsor. Revisions and the reasons for revisions will be recorded in the revised SAP. Ensure that the revised SAP be reviewed and approved in accordance with the same procedure as that for the original SAP.

The analysis will be conducted on all participant data after the database is locked.

9.1 Analysis Sets

Full Analysis Set (FAS): A dataset of participants who are randomized.

Pharmacokinetic Concentration Set (PKCS): A dataset comprising at least one post-dose effective test component concentration data obtained in participants who receive one dose of the investigational drug. The dataset is for descriptively statistical analysis of the PK concentration data.

Pharmacokinetic Parameter Set (PKPS): A dataset comprising PK parameter data obtained in participants who receive one dose of the investigational drug. The dataset is for descriptively statistical analysis of the PK parameter data.

Pharmacokinetic Similarity Set (PKSS): A dataset comprising data with at least one evaluable PK parameter. This dataset is the main data set for inferring whether the proposed biosimilar product and reference product are PK similar and in this trial. PK parameters of C_{max} and $AUC_{0-\infty}$ will be analyzed. The corresponding period data will not be included in the PKSS, when the conditions occur as following: 1) Participants who have positive results of ADA at baseline (0 h); 2) The first postdose sample provides C_{max} values; 3) The pre-dose (0 h) sample provides a quantifiable concentration value; 4) Concomitant medication occur during the trial and there is clear evidence that the combination medication has an effect on the pharmacokinetics (PK) of the investigational products.

Immunogenicity Analysis Set (IAS): A dataset comprising at least one post-dose effective test immunogenicity component data obtained in participants who receive one dose of the investigational drug. This dataset is used for the immunogenicity analysis.

Safety Set (SS): A dataset of participants who receive one dose of the investigational drug with evaluable safety data. This dataset is used for the safety analysis.

9.2 Analyses Supporting Primary Objective(s)

9.2.1 Statistical Model, and Method of Analysis

9.2.1.1 Pharmacokinetic Analyses

The PK parameters will be estimated based on the actual sampling time with Phoenix WinNonlin (Certara USA Inc, Version 8.4 or higher) using noncompartmental methods.

Pharmacokinetic parameters to be calculated include:

Parameter	Definition and Calculation
C_{max}	The maximum serum concentration; Observation
AUC_{0-t}	Area under the serum concentration versus time curve calculated to the last measurable observation (C_t); Linear trapezoidal method

Parameter	Definition and Calculation
AUC _{0-65days}	Areas under the serum concentration versus time curve calculated to 65 days postdose; Linear trapezoidal method
AUC _{0-∞}	Area under the serum concentration versus time curve extrapolated to infinity, calculated as AUC _{0-t} + C _t / K _{el}
T _{max}	Time to the maximum serum concentration; Observation
K _{el}	Elimination rate constant; calculated as the absolute terminal slope of the log-transformed concentration versus time curve
t _{1/2}	Terminal half-life; calculated as 0.693 / K _{el}
CL/F	Clearance; calculated as Dose / AUC _{0-∞}
V _d /F	Apparent distribution volume; Dose / (K _{el} × AUC _{0-∞})

For population included in PKCS, the concentration data of all participants measured for each time point will be used for descriptive statistics, including the number of cases, arithmetic mean, standard deviation, median, quartile, minimum, maximum, geometric mean and coefficient of variation. The individual and mean concentration - time curve (both in linear and semi-log scale) will be plotted. The upper standard deviations at each time point will be presented for the mean concentration – time curve.

For population included in PKPS, descriptive statistics of each PK parameter will be performed. The number of cases, arithmetic mean, standard deviation, median, minimum, maximum, geometric mean, coefficient of variation and coefficient of variation of geometric mean will be calculated for the PK parameters of C_{max}, AUC_{0-t}, AUC_{0-65days}, AUC_{0-∞}. The number of cases, arithmetic mean, standard deviation, median, minimum, maximum and coefficient of variations will be calculated for the PK parameters of T_{max}, t_{1/2}, K_{el}, V_d/F, and CL/F.

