	
two dosing regimens. Each participant will receive a single subcutaneous dose of either the proposed biosimilar product CHS-1420 or reference product HUMIRA® according to the randomization schedule. The details are as follows:
 
Administration:
 
Following an overnight fast of at least 10 hours, one of the investigational products will be administered to the participants on Day 1 under fasting conditions in the right lower quadrant (left lower quadrant, if necessary, and reason for different choice of injection site should be documented) of the participants' abdomen from 08:00 (± 1 h) in the morning in turn.
 
PK sampling:
 
A total of twenty-four (24) blood samples for each participant will be collected for determination of serum drug concentrations at 0 h (within 30 minutes pre-dose) and 2 h (Day 1), 4 h (Day 1), 8 h (Day 1), 12 h (Day 1), 24 h (Day 2), 36 h (Day 2), 48 h (Day 3), 60 h (Day 3), 72 h (Day 4), 96 h (Day 5), 120 h (Day 6), 144 h (Day 7), 168 h (Day 8), 216 h (Day 10), 288 h (Day 13), 360 h (Day 16), 528 h (Day 23), 696 h (Day 30), 864 h (Day 37), 1032 h (Day 44), 1200 h (Day 51), 1368 h (Day 58), 1536 h (Day 65) post-dose. Approximately 3.5 mL of blood will be collected at each sampling time point into vacutainer tubes containing a procoagulant followed by gentle inversions to get mixed up and then be left standing still till coagulation. The coagulated blood will be centrifugated and the serum will be transferred into two tubes and stored in a freezer at -70°C (temperature range: -90°C ~ -60°C) until analyzed.
 
Sampling for immunogenicity assessment:
 
A total of four (4) blood samples for each participant will be collected for determination of serum anti-drug antibodies (ADA) / neutralizing antibodies (Nab) at 0 h (within 30 minutes pre-dose) and Day 16, Day 30, Day 65 post-dose. Approximately 5 mL of blood will be collected at each sampling time point into vacutainer tubes containing procoagulant followed by gentle inversions to get mixed up and then be left standing still till coagulation. The coagulated blood will be centrifugated and the serum will be transferred into three tubes and stored in a freezer at -70°C (temperature range: -90°C ~ -60°C) until analyzed.
 
Safety tests:
 
Injection site assessment: within 1 h pre-dose and at 1 h, 4 h, 12 h, 24 h, 48 h post-dose.
 
Physical examination: on Day 65 before discharge from the trial. And also, a symptom-based physical examination will be performed on Day 4 before leaving the site.
 
Vital signs: within 1 h pre-dose and at 1 h, 2 h, 8 h, 12 h, 24 h, 48 h, 72 h post-dose, as well as on each OPV day.
 
Laboratory tests (chemistry, hematology, urinalysis, and coagulation function as well as pregnancy tests for female participants): on Day 4, Day 16, Day 30, and Day 65.

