	
degree of completion of the trial and withdrawal reasons. The relevant notes for data inclusion/exclusion should be recorded. Conditions in which data should be excluded can be as follows (not limited to):
 
 1) Data of participants who don't meet the inclusion criteria or meet the exclusion criteria, which may affect the results; 2) Data of participants who are incompliant with the clinical protocol during the trial, which should be judged rationally according to the severity of protocol deviations; 3) Data of participants with other behavior which may affect pharmacokinetics results during the trial; 4) After taking investigational product, the data of individual participants will be excluded from PK similarity analysis (PKSS) on condition that: 
 a. Participants who have positive results of ADA at baseline (0 h); b. The first postdose sample provides C_{max} values; c. The pre-dose (0 h) sample provides a quantifiable concentration value; d. Concomitant medication occur during the trial and there is clear evidence that the combination medication has an effect on the pharmacokinetics (PK) of the investigational products.
Termination Criteria	
 1) Refer to CTCAE 5.0, if more than half of the participants experience drug-related AEs of Grade 2, or more than a quarter of the participants experience drug-related AEs of Grade 3-4; or indication in which obvious intolerance; 2) Termination requested by the sponsor on the premise of full ensuring the legal rights and safety of participants; 3) Termination demanded by NMPA or Ethics Committee due to some reasons; 4) Other conditions in which the trial cannot be continued.
PK Evaluation	
The primary PK endpoints are the maximum serum drug concentration (C_{max}) and areas under the serum concentration versus time curve extrapolated to infinity ($AUC_{0-\infty}$).
 
The secondary pharmacokinetic endpoints are areas under the serum concentration versus time curve calculated to the last measurable observation (AUC_{0-t}) and to 65 days postdose ($AUC_{0-65\text{days}}$), the time to maximum serum concentration (observed) (T_{max}), the elimination half-life ($t_{1/2}$) and terminal elimination rate constant (K_{el}), apparent distribution volume (V_d/F) and clearance (CL/F).

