11 Sampling for immunogenicity assessment: A total of four (4) blood samples for each participant will be collected for determination of serum anti-drug antibodies (ADA) / neutralizing antibodies (Nab) at 0 h (within 30 minutes pre-dose) and Day 16, Day 30, Day 65 post-dose. The actual sampling time should be recorded;

12 Participants will be discharged from the clinical research facility after PK sampling and required safety assessment at approximately 72 h after dosing while OPVs are required at approximately 96 h (Day 5), 120 h (Day 6), 144 h (Day 7), 168 h (Day 8), 216 h (Day 10), 288 h (Day 13), 360 h (Day 16), 528 h (Day 23), 696 h (Day 30), 864 h (Day 37), 1032 h (Day 44), 1200 h (Day 51), 1368 h (Day 58), 1536 h (Day 65) post-dose;

13 Safety tests will be performed at the end of trial on Day 65 for each participant before discharge from the trial, including physical examination, laboratory tests [biochemistry, hematology, urinalysis, coagulation function, serum pregnancy test (only for females)], ECG, vital signs; and also the weight of participants will be collected;

14 Any dosed participants who withdraw ahead of time should receive the scheduled safety tests for permission to discharge from the trial before leaving or at the time of the participants next scheduled follow-up visit, or any other time appropriate in discretion of investigators. In addition collection of weight will be performed.

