4.2 Rationale for Trial Design

As a biosimilar product to Adalimumab, CHS-1420 of strength 40 mg/0.8 mL has been approved by FDA. Now an extended strength of 100 mg/mL CHS-1420, including 40 mg/0.4 mL and 80 mg/0.8 mL, will be declared. According to the guidance of Scientific Considerations in Demonstrating Biosimilarity to a Reference Product ^[4] and Clinical Pharmacology Data to Support a Demonstration of Biosimilarity to a Reference Product ^[1] issued by FDA as well as the PK and immunogenicity profile of the investigational products, the communication results with FDA on CHS-1420 of strength 40 mg/0.4 mL, this comparative PK is designed, the same way as that for PK similarity study of the lower concentration CHS-1420, as a single-center, randomized, single-blind, parallel-group trial with a single subcutaneous dose of either the proposed biosimilar product (T) CHS-1420 or reference product (R) HUMIRA® under fasting conditions. In addition, safety and

immunogenicity of the two products will be also evaluated and compared.

Study population: According to the guidance of Clinical Pharmacology Data to Support a Demonstration of Biosimilarity to a Reference Product issued by FDA, a study in healthy participants is considered to be more sensitive in evaluating the product similarity because it is likely to produce less PK and/or PD variability compared with a study in patients with potential confounding factors such as underlying and/or concomitant disease and concomitant medications. And healthy participants will be enrolled in this trial to assess the PK similarity between CHS-1420 and HUMIRA®.

Duration: The trial is expected to last 14 weeks including a 28-day screening period to enroll enough eligible participants. The test period will be approximately 10 weeks. According to the guidance of Clinical Pharmacology Data to Support a Demonstration of Biosimilarity to a Reference Product and PK profile of Adalimumab, this parallel trial is designed to sampling up to 65 days post dose which can cover the major PK behavior according to $t_{1/2}$ of Adalimumab (approximately 2 weeks).

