1.8 Sample Collection Time Point

A total of twenty-four (24) blood samples for each participant will be collected for determination of serum drug concentrations at 0 h (within 30 minutes pre-dose) and 2 h (Day 1), 4 h (Day 1), 8 h (Day 1), 12 h (Day 1), 24 h (Day 2), 36 h (Day 2), 48 h (Day 3), 60 h (Day 3), 72 h (Day 4), 96 h (Day 5), 120 h (Day 6), 144 h (Day 7), 168 h (Day 8), 216 h (Day 10), 288 h (Day 13), 360 h (Day 16), 528 h (Day 23), 696 h (Day 30), 864 h (Day 37), 1032 h (Day 44), 1200 h (Day 51), 1368 h (Day 58), 1536 h (Day 65) post-dose.

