4.3 Processing of Missing Data

For missing samples before the first quantifiable sample, the concentration values will be treated as “0”. For missing samples between the two quantifiable samples or after the last quantifiable sample, the concentration values will be treated as null listed as either “Not Reportable (NR)” or “No Sample (NS)”. No value will be reported and it will be just represented as “ND” which will be treated as missing data in the table for cases that PK parameters can't be acquired based on the concentration data. Other missing data may occur during safety assessment. Illogical data will be checked.

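### Does AUC0-65days run past the last blood sample, leaving the parameter without a defined end point?

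*Protocol*

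**What the plan says.** Protocol 9.2.1.1 and SAP 5.4.1 define AUC0-65days in the same words: "Areas under the serum concentration versus time curve calculated to 65 days postdose; Linear trapezoidal method". The endpoint lists in Protocol 1.1, Protocol 3.2 and SAP 2 say "and to 65 days postdose". Protocol 4.2 describes the design in the same terms: "this parallel trial is designed to sampling up to 65 days post dose".

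The sampling schedule gives hours. SAP 1.8, like the Protocol schedules, ends with "1368 h (Day 58), 1536 h (Day 65) post-dose". Protocol 1.1 fixes the day of dosing: "one of the investigational products will be administered to the participants on Day 1 under fasting conditions". The immunogenicity schedule in Protocol 1.3 (note 11) uses the same day labels for visits: "Day 16, Day 30, Day 65 post-dose".

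The handling rules that bear on the end of the curve are:

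- **Time basis** (Protocol 9.2.1.1, SAP 5.4.1): "The PK parameters will be estimated based on the actual sampling time".
- **Window for the last sample** (Protocol 1.3 note 10, SAP 4.2): ±240 min. A sample outside the window is recorded as a deviation.
- **Values below the LLOQ** (SAP 4.4): set to zero.
- **Missing samples** (Protocol 9.2.3, SAP 4.3): "after the last quantifiable sample, the concentration values will be treated as null". A parameter that the concentrations cannot support is shown as ND and treated as missing.

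**The concern.** An area to a fixed time needs that time as an input to the calculation. A visit can loosely be called Day 65, but a stated number of days after dosing reads as elapsed time, and here it falls a full day after the last scheduled sample. A trapezoid needs a concentration at its right-hand end, and there is none at 1560 h.

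Neither document gives the end time in hours, and the glossary in Protocol 14.1 lists AUC0-t and AUC0-∞ but not this parameter. One programmer could stop at the Day 65 sample while another enters 1560 h and extrapolates by a method neither document describes. The documents also do not say, for this parameter by name, what happens if the last sample is early, late or missing. At stake would be the reproducibility of a named secondary endpoint.

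**Working it through.** **Step 1. Day labels.** Dosing is on Day 1 and there is no Day 0, so study day = floor(hours / 24) + 1. All 23 post-dose labels follow this rule. For example, 24 h gives 1 + 1 = Day 2, 360 h gives 15 + 1 = Day 16, and 1536 h gives 64 + 1 = Day 65. The plan's own label is reproduced. Day 65 is a study day, and the sample is taken 1536 / 24 = 64.0 days after dosing.

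**Step 2. The literal end point.** 65 × 24 = 1560 h. The gap from the last scheduled sample is 1560 − 1536 = 24 h. The latest in-window sample is at 1536 + 4 = 1540 h (64.2 days), which leaves 20 h uncovered.

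**Step 3. What the stated method delivers.** The only method named is the linear trapezoid on actual times. With nothing drawn after the Day 65 visit, it stops at that sample.

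| Situation at Day 65 | Rule already in the documents | Result |
|---|---|---|
| Sample at 1532 h or 1540 h | actual sampling time | area ends at the real time |
| Value below the LLOQ | SAP 4.4 | enters as zero |
| Sample missing | null; ND if the parameter cannot be obtained | no value is invented; ND is the natural reading |

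**Step 4. Size if 1560 h were used.** The half-life of about 2 weeks is from Protocol 4.2. The rest is assumed: one compartment, first-order absorption, absorption half-lives of 1.5, 2.5 and 4 days, and elimination half-lives of 10 and 20 days as a range. With k and a the elimination and absorption rates, C(t) is proportional to exp(−kt) − exp(−at). The numerator is the area from 1536 to 1560 h; the denominator is the trapezoidal area over the 24 scheduled times.

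| Elimination half-life | Added by 1536–1560 h, % of AUC0-1536h |
|---|---|
| 10 days (assumed) | 0.09–0.13 |
| 14 days (documented) | 0.24–0.30 |
| 20 days (assumed) | 0.45–0.54 |

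A separate calculation used exact areas and assumed a Tmax of 4 to 8 days. It gives 0.23–0.27% at 14 days.

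A hand check agrees. With a 14-day half-life, one day removes 1 − 2^(−1/14) = 4.8% of the area still to come. With a Tmax of 5.5 days, 95.28% of the total area lies before 64 days and 4.72% after. So the added day is 0.048 × 4.72 / 95.28 ≈ 0.24% of the area to 64 days.

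**Step 5. Size of the window effect.** Moving the last sample from 1532 h to 1540 h changes the area by about 0.1% at 14 days.

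**Step 6. Where the parameter is used.** Protocol 9.2.1.1 and SAP 5.4.2 summarise it descriptively. The 90% confidence intervals in Protocol 9.2.1.2 and SAP 5.4.3 are for Cmax and AUC0-∞ only. AUC0-∞ is built from AUC0-t, the last measurable concentration and Kel, so the 65-day limit does not enter it.

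**The case for a change.** The strongest argument for acting is that the contradiction is plain arithmetic, repeated in both documents, and needs only rewording. That arithmetic stands: read literally, the limit is 1560 h and no compliant sample reaches it.

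The missing last sample is the more substantial part. Under the same model, the interval from 1368 h to 1536 h holds about 2–2.6% of the area at a 14-day half-life. A participant without the final sample could be reported short by that amount, extrapolated, or set to ND. It is also true that no sentence names this parameter when it describes ND.

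This does not amount to an undefined endpoint. Extrapolating would need a step the documents do not mention for this parameter. Reporting a shorter area under the 65-day name would ignore the general rule that a parameter the concentrations cannot support is ND. An analyst who applies the written rules arrives at one sensible answer.

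A tighter rule would bring little. Forcing the area to exactly 1536 h, or discarding a sample drawn slightly early, would address a difference of about 0.1% and could lose data. Protocol wording changes also need approval from the principal investigator, the sponsor and the ethics committee (Protocol 13.4).

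**Conclusion.** This is a clerical slip: a study-day label was written as elapsed time. The intended end point is the Day 65 sample at nominal 1536 h, 64 days after dosing. That is an inference from the schedules, but no other reading fits both the sampling times and the named method.

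The literal reading would change the parameter by about 0.24–0.30% at the documented half-life, and by 0.09–0.54% over assumed half-lives of 10 to 20 days. These percentages rest on the assumed one-compartment model and absorption rates, but the effect stays below 1% throughout that range. The parameter is secondary and descriptive, and Cmax, AUC0-∞ and the similarity conclusion do not depend on it. Following the plan as written gives sound results, so no change is needed.
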